With participant permission, we will collect complete and accurate contact information from the student at baseline, including home address, phone, cell phone, email, and phone numbers of three contacts and best times and days to reach them to maximize retention. A contact sheet will be completed by the participant that will include the above information. Care will be taken to maintain the confidentiality of the student's participation; therefore all students will be asked to provide us with the individuals or contact information where they feel comfortable being contacted by study staff or where they feel assured that the confidentiality of their participation will be maintained. The other contacts provided by the student will not be informed of the student's vaping status. We have found in prior studies that cell phone numbers and e-mail addresses are particularly helpful in remaining in contact with this population. Tracking procedures will be implemented for any student who does not attend a scheduled study visit or who is not accessible by telephone or e-mail at the contact location provided. Attempts to locate students will be made mainly through the schools and by telephone calls to the contacts provided or directory assistance.

Table 2. Study Assessments, Measures and Data Collection Timing

Variable and Measure	Relevant Aim	Baseline	6-month follow-up
Recruitment: # screened and eligible, # and reasons for refusal	2A	•	
Retention: # of dropouts, reasons for dropping out	2A		•
Engagement (V2V only): # of completed responses to texting quizzes, peer videos viewed, peer coaching interactions	2B		*
Acceptability and satisfaction: Client Satisfaction Questionnaire (CSQ-8) semi-structured interview	2B		•
Cotinine-validated 7-day point prevalence abstinence: saliva samples collected from all; analyzed for those reporting 7-day abstinence; cut-off 11.4 ng/ml	2C		•
E-cigarette use frequency (past 7 and 30 day) and intensity (# days and amount vaped in past 7 and 30 day)	2C	•	•
THC/marijuana and other tobacco use frequency (past 7 and 30 day) and intensity (# days and amount vaped)		•	•
Social Cognitive Theory (SCT) constructs			
Self-efficacy, confidence to quit: Self-efficacy Questionnaire (SEQ-12)		•	•
Demographics and tobacco use			
Demographics: age, gender, socio-economic status, race/ethnicity, grade in school, academic performance		•	•
History of all tobacco use, past and recent quit attempts, cessation strategies used		•	

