Data collection: Data collected from participants will be obtained through interviews, paper and pencil surveys, and collection of saliva samples for cotinine assessment by the Research Coordinator in-person at the school nurse office at baseline and 6-months post-study entry. The student survey and assessment tools for this study will be adapted from our prior adolescent smoking cessation trials and will be submitted to the IRB for review and approval prior to use in the study. Survey and assessment tools are described in Table 2 on page 10 of the ISP. Data confidentiality will be emphasized on the surveys and verbally by the Research Coordinator (see section #30), and by the use of a unique identification number. Data will be entered into the regulated environment through a secure Research Electronic Data Capture (REDCap) form. REDCap is a secure web application for building and managing online surveys and databases that was funded by the National Institutes of Health. REDCap data is also stored in a regulated environment. These files will be deleted after study completion. Portable devices used to collect data (audio and film recordings) will be UMMS-issued devices and files will not be encrypted during the recording, but the recordings will be transferred as soon as possible (i.e.: typically within the same day) to UMMS servers. Once the files are transferred, they will be deleted from the portable devices.

We will conduct biochemical verification using a saliva NicAlert® test (Nymox Corporation), which is a semi-quantitative method that uses a dipstick to measure the level of cotinine in a sample of saliva. The test strip displays the result in seven zones with each zone representing a range of levels of cotinine/smoking (e.g.: zone 0 [0 – 10 ng/mL, a nonsmoker] to zone 6 [>1000 ng/mL, a heavy smoker]). The results are read as 0-6, and as recommended, any value ≥ 1 is considered as tobacco use. Research staff will enter these values into the database, using the participant ID as an identifier, and destroy the samples.

Data Analysis:

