Aim 2C (Cessation Outcomes) *Hypothesis H2: The intervention will be associated with greater cotinine-validated 7-day point prevalence vaping abstinence rates, lower time to first quit attempt, and less amount of e-cigarette use compared to control at 6-month follow-up.* We recognize that there is some controversy about estimating effect sizes from pilot studies. However, we are calculating effect sizes in our study to provide a range, recognizing that there might be uncertainties because of our small sample size. To estimate effect sizes for V2V intervention versus control, between-condition differences over time will be estimated for **cotinine-validated 7-day point prevalence abstinence** using GEE logistic regression with a random effect for school and fixed effects of condition, time point (baseline and 6 months), and their interaction. Missing data is handled using inverse probability weighting. By taking the repeated measurements into consideration, the GEE model is able to increase the power to test the difference in the outcome. COX regression modeling will be used to examine the intervention effect on **time to first quit attempt** adjusting for other covariates. **Amount of e-cigarette use** will be calculated as a reduction from baseline. We will model this reduction using negative binomial regression modeling if the variance of the distribution of risk reduction is over dispersed.

Other information important for the design of a future study includes standard deviations, as well as **preliminary assessment of possible mediators** such as engagement, behavioral capability, and self-efficacy. We will identify important mediators in exploratory analyses. Guided by the conceptual model based on SCT, we will assess effects of intervention on the mediator and the

effects of the mediator on the outcome, controlling for other mediators in the model, and confounders of the mediator-outcome relationship, and then estimate the proportion of the intervention effect explained. Given the limited sample size, conclusions from the mediation analyses will be limited and treated with caution, but modeling will allow us to explore the constructs of SCT and potential predictors towards a larger RCT.

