or older, and the video release form that there is no limit on the length of time we will store the peer videos and that it is possible that we might use the peer videos in future iterations of the V2V Intervention.

Data collected from participants will be obtained through interviews, paper and pencil surveys, writing sessions, and collection of saliva samples for cotinine assessment by the Research Coordinator, in-person at the school nurse office at baseline and 6-months post-study entry. Data confidentiality will be emphasized on the surveys and verbally by the Research Coordinator, and by the use of a unique identification number. Data will be entered into the UMMS regulated environment through a secure Research Electronic Data Capture (REDCap) form. Data (excluding peer videos) will not be distributed. Peer videos will be distributed to study participants via a secure website (example: Vimeo), and will be password protected. With the exception of the peer videos, we will retain study records and documents for a period of 3 years after the completion of the study.

See also #13, *Data Analysis and Management*.

Protection for Risks Associated with Potential Loss of Confidentiality

The study team have systems, oversight, experienced personnel, and an organizational culture that supports the appropriate use, access and storage of confidential information. All persons collecting or handling data will be trained in human subjects' procedures, confidentiality and privacy protection. All investigators and project staff are required to receive and complete Human Subjects and HIPAA training. All research personnel will hold a current Human Subjects Training Certificate.

Because the study will be funded by the NIH, we will follow the guidelines in the NIH certificate of confidentiality. The certificate keeps us from sharing identifiable sensitive information collected for the research unless the participants allow us to do so. This is included in the assent and consent form that was included as part of this IRB application. We will only disclose information about the students if they plan to harm themselves or others, or if they have a clinically significant score on the psychosocial factors scales included in the baseline and follow up data collection forms. We will not be disclosing information about illicit drugs issues to law enforcement agencies, parents, the school, or others.

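### H2's abstinence analysis does not say which contrast it reports, and the plan is inconsistent on baseline saliva, the cotinine cut-off and the school model

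*Combined protocol and SAP*

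**What the plan says.** **Hypothesis and model.** H2 (Section 4, repeated in Section 13, Aim 2C) compares V2V with control at the 6-month follow-up. For validated abstinence, Section 13 describes the effect size as a between-condition difference over time. It comes from "GEE logistic regression with a random effect for school" and "fixed effects of condition, time point (baseline and 6 months), and their interaction". Section 13 adds: "By taking the repeated measurements into consideration, the GEE model is able to increase the power to test the difference in the outcome". Neither Section 10 nor Section 13 says which model term, or which combination of terms, is the effect size.

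**Timing of the measure.** Table 2 (Section 11) marks validated abstinence at 6 months only, with this definition: "saliva samples collected from all; analyzed for those reporting 7-day abstinence; cut-off 11.4 ng/ml". Section 13, Aim 2 Data collection, says the study will collect "saliva samples for cotinine assessment by the Research Coordinator in-person at the school nurse office at baseline and 6-months post-study entry". Section 26 says the same: "saliva samples for cotinine assessment by the Research Coordinator, in-person at the school nurse office at baseline and 6-months post-study entry".

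**Threshold.** Section 13 specifies a semi-quantitative dipstick read in zones 0 to 6, with zone 0 covering 0 to 10 ng/mL, and "any value ≥ 1 is considered as tobacco use". Staff record the zone reading and then destroy the sample.

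**The concern.** Two different quantities could be reported as the H2 abstinence effect: the odds ratio at 6 months, or the condition-by-time interaction. H2's wording points to the first. The description of the model, as a difference over time with an interaction, points to the second.

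The second also depends on a baseline value that the plan both schedules and does not schedule. In addition, two rules define who counts as abstinent, and one of them cannot be applied with the stated test. The school term names a feature that the stated method does not have.

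Section 13 presents these effect sizes as a range, alongside other information for designing a larger study. A planner needs to know which quantity the range describes and how abstinence was defined.

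**Working it through.** **1. The plan's own figure.** The only sample-size figure concerns retention (H1, Section 13). The design effect is 1 + 0.01 × (20 − 1) = 1.19, and 40/1.19 = 33.6, rounded to 34. The exact 95% CI for 29/34 is 68.9% to 95.0%, as stated. It has no bearing on H2, for which the plan gives no rates, effect or power. From the documents I use 40 per arm at baseline and 40 × 0.85 = 34 per arm at 6 months (Section 25). All abstinence rates below are assumptions.

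**2. The two contrasts.** Write logit P(abstinent) = b0 + b1·condition + b2·time + b3·condition×time.
- 6-month log odds ratio = b1 + b3.
- Interaction b3 = 6-month log odds ratio − baseline log odds ratio.

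Assume 10% (control) and 20% (V2V) abstinent at 6 months. The 6-month odds ratio is (0.20/0.80)/(0.10/0.90) = 2.25. The interaction, as a ratio of odds ratios, depends on baseline:

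| Baseline, control | Baseline, V2V | Ratio of odds ratios |
|---|---|---|
| 10% | 10% | 2.25 |
| 5% | 10% | 2.25/2.11 = 1.07 |
| 10% | 5% | 2.25 × 2.11 = 4.75 |

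The two quantities agree only when the baseline odds are equal.

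**3. Is there a baseline value?** Table 2 leaves the baseline cell blank for validated abstinence, as it does for retention. Section 23 mentions cotinine validation with the 6-month assessments, without excluding baseline. Sections 13 and 26 collect saliva at both visits. Baseline self-report exists either way, because Table 2 records "E-cigarette use frequency (past 7 and 30 day) and intensity" at both visits. The conflict is over the validated value. If Table 2 governs, b2 and b3 cannot be estimated.

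**4. If baseline values exist but abstinence is rare.** Section 6 admits anyone with use in the past 90 days, so baseline 7-day abstinence is possible but may be uncommon. With 40 per arm and a baseline rate p in both arms, ignoring school clustering:

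P(at least one arm has no baseline abstainers) = 1 − [1 − (1 − p)^40]².

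| p (assumed) | (1 − p)^40 | Probability |
|---|---|---|
| 2.5% | 0.363 | 59% |
| 5% | 0.129 | 24% |
| 10% | 0.015 | 3% |

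An empty arm leaves the interaction without a finite estimate. A constructed data set with no baseline abstainers, and 3/34 against 7/34 abstinent at 6 months, gave an intercept near −26.6 and no usable standard error for condition or interaction. From the same 6-month data alone, the odds ratio is (7/27)/(3/31) = 2.68, 95% CI 0.63 to 11.4.

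**5. The cut-off.** Under the strip rule, use means above 10 ng/mL. Under Table 2 the threshold is 11.4 ng/ml. No stated zone boundary lies at 11.4, and once the sample is destroyed the value cannot be recovered. The rules disagree for samples between 10 and 11.4 ng/mL from participants who report abstinence. In the 3/34 against 7/34 example, one such sample moves an arm by 1/34 = 2.9 percentage points:
- In control: (7/27)/(4/30) = 1.94.
- In V2V: (8/26)/(3/31) = 3.18.

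The number of such samples cannot be derived from the documents.

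**6. Schools.** A GEE estimates a marginal model with a working correlation and a robust variance. It has no random effects. A random school effect belongs to a mixed model. The sentence therefore does not identify a model that can be fitted.

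**The case against.** Several points on the other side stand.

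- **The effect is not wholly undefined.** H2 fixes the comparison at 6 months, a logistic model implies an odds-ratio scale, and the stated model yields the 6-month contrast as b1 + b3. What is missing is one sentence choosing between two contrasts.
- **Table 2 may be the outlier.** Sections 13 and 26 and the model itself point to baseline collection, and a table mark may have been lost in text extraction. The interaction is therefore inestimable on one reading only.
- **The strip rule works on its own.** A reading of 1 or more is a complete definition. The shifts to 1.94 or 3.18 lie well inside the interval of 0.63 to 11.4.
- **The intent on schools is plain.** For retention, Section 13 uses a GEE to allow for school clustering.
- **Imprecision is disclosed.** Section 13 says that pilot effect sizes are imprecise. That covers sampling error, though not which quantity is estimated.

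A reader might also infer three stronger claims that the documents do not support.

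- **That the two contrasts would point in opposite directions.** One can construct this: 2/40 against 6/40 at baseline with 3/34 against 7/34 at 6 months gives 2.68 and 2.68/3.35 = 0.80. But the 0.80 has a 95% CI of about 0.09 to 7.3 at zero within-person correlation, so it favours neither arm. In simulations at assumed true rates of 10% against 20%, the signs differed in 8% to 15% of trials with finite estimates. At 2.5% baseline only about 40% of trials were finite, and in the low-baseline settings checked (2.5% to 5%) the 6-month estimate alone had the wrong sign in about 9% of finite trials. Much of the disagreement may be small-sample noise.
- **That the power sentence is false.** It is unsupported, because it names no comparator, rates or correlation. At 10% against 20% with 10% baseline abstinence, the interaction is more precise than a 6-month-only analysis if the within-person correlation exceeds 0.57, and less precise below that.
- **That covariate adjustment is required.** With few events it is a matter of judgement.

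**Conclusion.** The point holds as a set of gaps and contradictions in the text, and it should be fixed before the H2 abstinence analysis is run. Three parts need no assumed rates: the contrast is not chosen, the cut-off cannot be applied with the stated strip, and the school term does not fit a GEE. The baseline conflict also stands on the text. Its consequence depends on which statement governs: no estimate of the interaction under Table 2, or a 59% to 24% chance of no finite estimate if baseline abstinence is 2.5% to 5% (assumed, 40 per arm, clustering ignored). At 10% that chance is only 3%.

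The size of the cut-off problem is unknown. Nothing here shows that the trial's conclusion on H2 would change direction. Section 10 makes the outcome secondary, so H1, the retention target and the sample size are unaffected.

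**What to change.** 1. In Section 13, Aim 2C, name the 6-month between-condition odds ratio as the H2 abstinence effect, with each arm's proportion and a 95% CI. It needs no baseline saliva. The planned inverse probability weighting can stay.
2. Use one cotinine rule in Table 2 and Section 13 that the stated test can apply. If the strip is kept, this is the zone reading. Keeping 11.4 ng/ml would require a named quantitative assay.
3. Replace the school wording with one valid model: a mixed logistic model with a random school intercept, or a GEE clustered on school with a small-sample correction. State that so few schools (four in Section 25, four to seven in Section 6) limit either one.
4. Reconcile Table 2 with Sections 13 and 26 on whether saliva is taken at baseline.

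Optional: delete the power sentence or give its comparator and conditions; and add an estimate adjusted for one baseline use measure, labelled separately because the adjusted odds ratio is a different quantity. Expected events are only 34 × (0.10 + 0.20) = 10.2 at 10% against 20%, or 34 × (0.05 + 0.10) = 5.1 at 5% against 10%, so no more than one covariate.

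The cost is a few sentences and one table row, unless a quantitative assay is chosen. The statistical price is that dropping the interaction gives up a difference-in-change answer to baseline imbalance. Such imbalance is plausible with about two schools per condition, and an adjusted estimate would only partly replace that answer.

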10. STUDY ENDPOINTS*

The primary outcome for Aim 2 is the feasibility of the research protocols, including participant recruitment and retention. Secondary outcomes include: preliminary effect size estimates of the intervention on cotinine-validated 7-day point prevalence abstinence, time to first quit attempt, and amount of use; acceptability of and satisfaction with the intervention; system use and adoption of cessation supporting strategies; Social Cognitive Theory (SCT) constructs; and demographics and tobacco use.

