Aim 2A (Feasibility) Hypothesis H1: *We will be able to recruit 80 adolescents (20/school, 40 per study condition), and $\geq 85\%$ will be retained in each study condition at 6-month follow-up.* We will estimate recruitment rates, overall and per condition. Also, for each condition, we will model 6-month retention, using generalized estimating equation (GEE) logistic regression to account for within-school clustering and dependence over time.

Proposed Sample Size. As appropriate for a pilot study, we are estimating our power and sample size based on the feasibility hypothesis (H1). Because pilot studies do not provide meaningful estimates of effect sizes due to the imprecision inherent in small samples, we base our proposed sample size of 40 students per condition (20 per school) on obtaining precision in estimating condition-specific retention rates, providing important information for design and recruitment for the future R01 study. Based on our prior study of adolescent smoking cessation, estimated intra-school correlation=0.01, for a design effect due to within-school clustering of $1 + [0.01 \times (20 - 1)] = 1.19$, and an effective sample size per condition of $40/1.19 = 34$. Based on our prior studies in

adolescents in school settings, we anticipate at least 85% retention. Thus, a conservatively wide 95% exact CI for per-condition retention rate is (68.9%, 95.0%).

Aim 2B (Monitor V2V Engagement and Assess Program Satisfaction) As the trial progresses, we will monitor engagement overall and by participant subgroups (e.g. by gender, race, age) as a formative assessment. Then, as the trial ends, we will also use this information as a component of our summative evaluation. We anticipate that engagement will lead to positive changes in acceptability, and satisfaction, and cessation.

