25. LOCAL NUMBER OF SUBJECTS

The local number of subjects for this study is as follows:

Aim 1: 20 adolescent e-cigarette users (peer advisory panel) and 2 key informants (school nurse and vice principal) from 1 high school.

Aim 2: 80 adolescent e-cigarette users from four high schools selected for their high rates of racial/ethnic minorities and low SES status (20/school, 40/study condition) will be recruited and complete assessments at baseline and 6-month follow-up. With a conservative 85% retention rate, we will achieve a total of 68 e-cigarette users (17/school, 34/study condition) at 6-month follow-up. We will also recruit up to 12key informants (school nurses, vice principal, or other academic administrator) from participating high schools.

Overall, we plan to recruit up to 110 individuals.

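### Missing 6-month abstinence is handled only by inverse probability weighting, and no planned analysis shows how the result changes if students who were lost are more often still vaping

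*Combined protocol and SAP*

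**What the plan says.** Section 13, Aim 2C, analyses validated 7-day abstinence by GEE logistic regression with "fixed effects of condition, time point (baseline and 6 months), and their interaction". The rule for missing outcomes is "Missing data is handled using inverse probability weighting". The variables in the weight model are not listed, and the plan does not say whether condition is among them. No section describes an analysis under a different assumption about dropouts.

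Table 2 in Section 11 schedules validated abstinence at the 6-month visit, and no study assessment falls between baseline and that visit. The process data that might help predict dropout are listed for one arm only: "Engagement (V2V only): # of completed responses to texting quizzes, peer videos viewed, peer coaching interactions".

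On expected losses, Section 13 says "we anticipate at least 85% retention", and Section 25 says "With a conservative 85% retention rate, we will achieve a total of 68 e-cigarette users (17/school, 34/study condition) at 6-month follow-up". Retention is to be modelled separately in each condition (Section 13, Aim 2A), and Table 2 records the number of dropouts and their reasons.

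On the status of the outcome, Section 10 states: "Secondary outcomes include: preliminary effect size estimates of the intervention on cotinine-validated 7-day point prevalence abstinence". Aim 2C adds: "we are calculating effect sizes in our study to provide a range, recognizing that there might be uncertainties because of our small sample size".

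**The concern.** A student who misses the 6-month visit has no abstinence result. Weighting replaces that student with completers who look similar on the weight variables, and so assumes the same quit rate. In a cessation study, continued vaping is a plausible reason for not coming back, and the trial's own data cannot test whether that happens.

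Three features make the assumption hard to lean on here. First, at the planned retention only about 12 students are lost, which supports a very small dropout model. If its variables are left open, they may be chosen after the data are seen. Second, a weight model common to both arms is largely limited to baseline data. Third, V2V students receive periodic coach texts while control students receive written materials, so a retention gap between arms is plausible.

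At stake is the abstinence contrast that the plan wants to report as a range. The plan attributes its uncertainty to small sample size. A sampling interval does not include uncertainty about students who were never measured.

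**Working it through.** **1. The plan's own figures.** Inputs from Section 13 (Aim 2A) and Section 25: 80 students, 40 per condition, 20 per school, intra-school correlation 0.01, retention 85%.
- Design effect = 1 + 0.01 × (20 − 1) = 1.19. Effective size = 40/1.19 = 33.6, about 34.
- The exact (Clopper-Pearson) 95% interval for 29/34 is 68.9% to 95.0%, as the plan states.
- Completers: 80 × 0.85 = 68, or 34 per condition, also as stated. That leaves 6 lost per condition, 12 in all.

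No quit rate is given for abstinence, so there is no figure for that outcome to reproduce.

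**2. Bias if dropouts are still vaping.** These are assumptions, not document figures: the same true abstinence p in both arms (no effect), every dropout vaping, and weights that return the completer rate in each arm. With retention r, the completer rate is p/r. The spurious difference (V2V minus control) is p/r_V − p/r_C.

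| True abstinence p | Retention V2V / control | Completer rates | Spurious difference | Odds ratio |
|---|---|---|---|---|
| 15% | 80% / 90% | 18.8% / 16.7% | +2.1 points | 1.15 |
| 20% | 80% / 90% | 25.0% / 22.2% | +2.8 points | 1.17 |
| 25% | 80% / 90% | 31.3% / 27.8% | +3.5 points | 1.18 |
| 15% | 75% / 90% | 20.0% / 16.7% | +3.3 points | 1.25 |
| 25% | 75% / 90% | 33.3% / 27.8% | +5.6 points | 1.30 |

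With 90% / 80% the differences are −2.1, −2.8 and −3.5 points. With 85% / 85% they are zero.

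**3. Whether a 10-point gap is far-fetched.** If true retention is 85% in both arms (independent binomials, 40 per arm, clustering ignored), a gap of 10 points or more (at least 4 students) arises by chance about 27% of the time.

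**4. How much the missing results leave open.** With 6 of 40 unknown in each arm, the most extreme assignments of the missing outcomes give a difference that spans 6/40 + 6/40 = 30 points. Take an assumed 8 versus 4 validated quitters:
- 34 and 34 retained: completers give 8/34 − 4/34 = +11.8 points; missing counted as vaping gives 8/40 − 4/40 = +10.0; extremes −5.0 to +25.0.
- 32 (V2V) and 36 (control) retained: 8/32 − 4/36 = +13.9 points; missing as vaping +10.0; extremes 0.0 to +30.0.
- 36 and 32 retained: 8/36 − 4/32 = +9.7 points; missing as vaping +10.0; extremes −10.0 to +20.0.

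**The case against.** A reader might infer that any retention difference between arms is inseparable from a V2V effect. The documents do not support that. If dropout is unrelated to 6-month vaping given the weight variables, and the weights account for condition, a retention gap alone causes no bias. For example, with 25% abstinent among completers in both arms and retention of 90% versus 80% (assumed), weighting gives an odds ratio of 1.00. Counting the missing as vaping gives 22.5% versus 20.0%, an odds ratio of 1.16, or 0.86 with retention reversed. In that example it is the alternative method that turns a retention gap into an apparent effect. Bias under weighting needs dropout that depends on unmeasured vaping status. It can also occur with equal retention if that dependence differs by arm.

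A reader might also infer that counting the missing as vaping is the right answer. It is just as untestable. Eligibility requires only some e-cigarette use in the past 90 days (Section 6), and the programme also serves students who are not ready to quit (Section 5). Some may already be abstinent for 7 days at entry.

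The plan has safeguards. Retention is modelled by condition and dropout reasons are recorded. Contact details, tracking of missed visits, and a $25 gift card per assessment are not limited to V2V. A retention gap would therefore be visible. The shift is also small against sampling error: 9/40 versus 8/40 gives an odds ratio of 1.16 with a 95% interval of about 0.40 to 3.40 (Wald, clustering ignored). Section 13 also says that pilots do not give meaningful effect sizes and explains that "we base our proposed sample size of 40 students per condition (20 per school) on obtaining precision in estimating condition-specific retention rates". No section says this contrast will set the effect size of the future R01.

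All of this stands and limits the severity. It does not supply the missing analysis: a visible gap in retention still comes with no result showing what it does to the abstinence estimate.

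**Conclusion.** The concern holds in a limited form. Weighting is the only stated method, it rests on an assumption the data cannot check, its variables are not named, and nothing planned shows how sensitive the abstinence contrast is to that assumption. Under the assumptions in the working, a 10-point retention gap shifts the contrast by about 2.1 to 3.5 points in either direction, and a 15-point gap by about 3.3 to 5.6 points. With equal retention and no true effect there is no shift. These sizes depend on every dropout vaping and on weights that recover only the completer rate. A weaker link between vaping and dropout, or informative weights, would make them smaller.

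Severity is minor to moderate. The outcome is secondary and preliminary, and the primary outcome is feasibility. The change is still worth making, because the stated purpose is a range, and a range that leaves out dropout uncertainty is too narrow.

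**What to change.** Keep the weighted analysis and state its weight model in Aim 2C, including at least condition and baseline e-cigarette use. Whether V2V engagement data also enter through arm-specific weights is a choice for the sponsor, but it should be written down before outcomes are seen.

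Add two pre-specified sensitivity analyses on all enrolled students, grouped by school of enrolment:
- Count every student without a validated 6-month abstinence result as vaping. This includes anyone who reports abstinence but has no saliva result, a case the plan does not cover.
- Vary the assumed abstinence among dropouts separately in each arm, both below and above that arm's completer rate, and report the range of the arm contrast.

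Present both beside the weighted result and retention by arm, as sensitivity results and not as the correct answer. The cost is a few sentences and two extra model runs, with no new data. The downside is that abstinence may look slightly lower when missing counts as vaping: for example, an assumed 10 quitters would read 10/40 = 25% instead of 10/34 = 29%.
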